7.2.1.2. Clinical Outcome and Response at TOC and Follow-Up

Clinical outcome and response are evaluated at participant level at the TOC and FU Visits. The criteria for clinical outcome and response are defined in [Table 8](#) (TOC) and similarly in [Table 11](#) (FU).

Table 11 Clinical Outcome and Response at the Follow-Up Visit

Defining Criteria	Outcome	Response
Participants who withdraw from the study prior to the FU Visit will be considered not achieving success (imputed as failure) as the clinical response at FU.		
Resolution of signs and symptoms of acute cystitis demonstrated at the TOC Visit persist at the FU Visit (and no new signs and symptoms), without the participant receiving other systemic antimicrobials before the FU Visit.	Sustained clinical resolution	Clinical success
Resolution of signs and symptoms of acute cystitis present at Baseline (and no new signs or symptoms), after clinical failure at TOC, without the participant receiving other systemic antimicrobials before the FU Visit.	Delayed clinical resolution	Clinical failure
Improvement in total symptom scores from Baseline, but not complete resolution, without the participant receiving other systemic antimicrobials before the FU Visit.	Clinical improvement	Clinical failure
Worsening or no change in total symptom scores at FU compared to Baseline after clinical failure at TOC or the participant received other systemic antimicrobials for the current infection before or on the date of the FU Visit	Clinical worsening	Clinical failure
Signs and symptoms of acute cystitis reoccur at the FU Visit assessment after clinical success at the TOC Visit	Clinical recurrence	Clinical failure
1) The baseline score is missing or 2) The FU assessment is missing or 3) The participant received other systemic antimicrobials not for the current infection before the FU Visit (unless clinical worsening or recurrence outcome criteria were met)	Unable to determine	Clinical failure

TOC=Test-of-Cure. FU=Follow-up.

If participant took both other systemic antimicrobials for the current infection on or before the date of the FU Visit, and other systemic antimicrobials not for the current infection before the date of the FU Visit, then participant outcome will be derived as ‘Clinical worsening’.

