Improvement in total symptom scores from Baseline, but not complete resolution, without the participant receiving other systemic antimicrobials before the Follow-up Visit	Clinical improvement	Clinical failure
Worsening or no change in total symptom scores at Follow-up compared to Baseline after clinical failure at TOC, or the participant received other systemic antimicrobials for the current infection before or on the date of the Follow-up Visit	Clinical worsening	Clinical failure
Signs and symptoms of acute cystitis reoccur at the Follow-up Visit after clinical success at TOC	Clinical recurrence	Clinical failure
1) The Baseline score is missing, or 2) The Follow-up assessment is missing, or 3) The participant received other systemic antimicrobials not for the current infection prior to the assessment (unless the clinical worsening or recurrence outcome criteria were met)	Unable to determine	Clinical failure

TOC = Test-of-Cure

- a. A study physician or otherwise appropriately medically trained staff will determine the individual clinical signs and symptoms scores for acute cystitis ([Appendix 6](#)), which will then be used to programmatically determine the clinical outcome. The same scorer will be used at all assessment time points for each participant, on all occasions, whenever possible.

CCI

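### At Follow-up, an untreated recurrence scoring below Baseline meets both clinical improvement and clinical recurrence, and no rule ranks the two

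*SAP*

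**What the plan says.** Clinical outcome at TOC and Follow-up is a secondary endpoint (SAP Section 2.2). Its summary measure is the percentage of participants in each outcome category, by arm (SAP Table 1). Protocol Section 8.1.3.1 has the outcome determined programmatically from the symptom score. The Follow-up categories are in SAP Table 11, with equivalent criteria in protocol Table 11.

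- Improvement: "Improvement in total symptom scores from Baseline, but not complete resolution, without the participant receiving other systemic antimicrobials before the FU Visit". The protocol row reads "Improvement in total symptom scores from Baseline, but not complete resolution, without the participant receiving other systemic antimicrobials before the Follow-up Visit". Neither mentions TOC status.
- Recurrence: "Signs and symptoms of acute cystitis reoccur at the FU Visit assessment after clinical success at the TOC Visit".
- Worsening, score branch: "Worsening or no change in total symptom scores at FU compared to Baseline after clinical failure at TOC".
- Worsening, antimicrobial branch: "the participant received other systemic antimicrobials for the current infection before or on the date of the FU Visit".
- Delayed resolution: "Resolution of signs and symptoms of acute cystitis present at Baseline (and no new signs or symptoms), after clinical failure at TOC".

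SAP Table 11 contains two tie-breaks. Under unable to determine, an antimicrobial taken for another infection leads to that category "unless clinical worsening or recurrence outcome criteria were met". A note under the table covers participants who took antimicrobials both for the current infection and for something else; "then participant outcome will be derived as" clinical worsening.

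**The concern.** Sustained resolution and recurrence describe participants who had resolved at TOC. Delayed resolution and score-based worsening describe those who had failed at TOC. Improvement is the only score-based row with no TOC condition, so it reaches into the group that recurrence is meant to describe.

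The neighbouring microbiology tables do this more carefully. In SAP Table 9 every row based on a culture result is conditioned on TOC status, and SAP Table 10 states which outcome yields when several apply. The gap in Table 11 therefore looks like an omission.

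What is at stake is a descriptive result. A participant who was symptom-free at TOC and then relapsed could be reported as improved, which hides the loss of durability that the Follow-up Visit can show. The categories feed the clinical outcome summaries in the ITT and micro-ITT NTF-S Populations (SAP Section 7.2.6.1), the stacked bars of clinical outcome (Section 7.2.6.4), and Table 2.21, a headline deliverable if the study continues (Section 11.9.7). Stacked bars presuppose one category per participant.

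**Working it through.** The plan states no figure on this point, so there is none to reproduce. The check is to write the rows as conditions and enumerate.

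**Inputs.** Four symptoms, each scored 0 to 3, so totals run from 0 to 12; Baseline total B is at least 2; TOC success requires a total of 0 (all SAP Section 7.1.1.3). F is the Follow-up total. 'Untreated' below means no other systemic antimicrobial before Follow-up.

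| Category | TOC status | Score at Follow-up | Other systemic antimicrobial |
|---|---|---|---|
| Sustained resolution | resolved | F = 0 | none before Follow-up |
| Delayed resolution | failure | F = 0 | none before Follow-up |
| Improvement | not stated | 0 < F < B | none before Follow-up |
| Worsening, score branch | failure | F ≥ B | not restricted |
| Worsening, antimicrobial branch | not stated | any | for current infection, before or on the visit date |
| Recurrence | success | F > 0 | not restricted |

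**Untreated participants with TOC success.**

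- F = 0: sustained resolution only.
- 1 ≤ F ≤ B − 1: improvement and recurrence.
- F ≥ B: recurrence only.

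Recurrence pairs: 11 Baseline totals (2 to 12) × 12 Follow-up totals (1 to 12) = 132.
Pairs also meeting improvement: sum of (B − 1) for B = 2 to 12 = 1 + 2 + … + 11 = 66, that is 66/132 = 50%.

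**How the share varies.** At a given Baseline it is (B − 1)/12: 1/12 = 8% at B = 2 and 11/12 = 92% at B = 12. By the Baseline bands in SAP Section 5.4.2:

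- 2–5: 10/48 = 21%
- 6–8: 18/36 = 50%
- 9–12: 38/48 = 79%

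Weighting all eligible four-item symptom profiles equally, instead of total scores, gives 46%. If recurrences are assumed mild, the share of pairs rises: 21/22 = 95% for F ≤ 2, 30/33 = 91% for F ≤ 3, 38/44 = 86% for F ≤ 4, and 51/66 = 77% for F ≤ 6. These are shares of possible scores and say nothing about how often each occurs.

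**Effect on the reported percentage.** Let R be the percentage of participants with TOC success and symptoms at Follow-up, and d the fraction of them that meet both rows. Setting aside the overlap with worsening, reported recurrence lies between R(1 − d) and R, depending on how the program resolves the overlap. The documents give neither R nor d.

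**The tie-breaks.** The first ranks worsening and recurrence above unable to determine. The second concerns participants who took both kinds of antimicrobial. Neither ranks improvement against recurrence.

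**With improvement restricted to TOC failures.** The 66 untreated double classifications fall to 0, and every antimicrobial-free combination maps to exactly one category. Overlaps remain for participants treated for the current infection:

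- Recurrence and worsening after TOC success: 132 combinations if treated before Follow-up and 132 if treated on the visit date.
- On the visit date, worsening also overlaps improvement (66), sustained resolution (11) and delayed resolution (11).

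These counts read the antimicrobial branch of worsening as independent of TOC status. The alternative, that it too requires TOC failure, would leave a symptom-free TOC success who was treated for the current infection before Follow-up with no category at all.

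**The case against.** The strongest reply is that this changes nothing that matters. Improvement and recurrence are both clinical failures, so clinical and therapeutic response at Follow-up are the same whichever is assigned. The outcome percentages are descriptive and by arm, with no direct comparison (SAP Section 2.2.2) and no formal testing (Section 7.2.6.1). Any convention would apply equally to both arms. Response is reported at both TOC and Follow-up, and outcomes are listed by participant (Listing 17), so a fall in success between visits stays visible. The structure of the table also signals the intent: going from 0 at TOC to a positive score is deterioration, and a programmer would probably choose recurrence.

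All of this limits the consequence and stands. It does not supply the missing rule. The outcome category is an endpoint in its own right, and a programmatic derivation needs to know which value to return.

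A reader might go further and infer that nearly every recurrence is double-classified, so that reported recurrence could fall to almost nothing. The documents do not support that. It would need recurrences to be mild relative to Baseline, and no Follow-up score distribution is given. Recurrences at or above the Baseline score meet recurrence and not improvement. Recurrences treated with another systemic antimicrobial before Follow-up cannot meet improvement at any score, and Protocol Section 4.1 allows symptomatic participants to return and be treated at any time.

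A reader might also infer that improvement wins because it is listed before recurrence. Nothing makes row order the precedence. SAP Table 10 lists recurrence before persistence yet makes recurrence yield to it.

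**Conclusion.** The concern holds in a limited form. Any recurrence after TOC success that scores below Baseline, with no other systemic antimicrobial before Follow-up, meets two categories in both SAP Table 11 and protocol Table 11, and no stated rule chooses between them. The categories of a descriptive secondary endpoint are therefore not mutually exclusive, and recurrence can be understated.

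The size cannot be derived from the documents. The neutral count of possible scores (46% to 50% overlapping, 8% to 92% by Baseline score) shows that the overlap is not a corner case, but it does not estimate how many participants are affected. The only durability figure in the documents, symptom resolution in 19 of 22 participants at TOC and 18 of 22 at Follow-up in the Phase IIa study (Protocol Section 2.1), is a net change and carries no score information.

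The primary analysis, clinical response, therapeutic response and all formal tests are unaffected. This is a minor correction, worth making because it removes an arbitrary programming choice.

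**What to change.** In SAP Table 11 and protocol Table 11, restrict the clinical improvement row to participants who were clinical failures at TOC, matching delayed resolution and score-based worsening.

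That alone does not make the categories exclusive. Add one sentence under each table giving the order of precedence among the remaining overlaps. It should state in particular whether a participant with TOC success and symptoms at Follow-up, who received a systemic antimicrobial for the current infection, is counted as worsening or recurrence. It should also cover antimicrobials started on the date of the Follow-up Visit.

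The cost is a few words and one sentence in each document, settled before unblinding. No data collection, sample size or test changes.

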7.2.1.3. Therapeutic Response at Follow-up

A therapeutic success at Follow-up refers to participants who have been deemed both a “microbiological success” and a “clinical success” at the Follow-up Visit. All other combinations will be deemed failures for therapeutic response.

7.2.2. Summary Measure

For details of the estimand summary measure see [Table 1](#) in Section [2.2.2](#).

7.2.3. Population of Interest

For details of the estimand population see [Table 1](#) in Section [2.2.2](#).

7.2.4. Strategy for Intercurrent Events

For details of the estimand strategy for intercurrent events see [Table 1](#) in Section [2.2.2](#).

7.2.5. Treatment Condition

For details of the estimand treatment condition see [Table 1](#) in Section [2.2.2](#).

7.2.6. Statistical Analyses / Methods

7.2.6.1. Statistical Methodology Specification

There will be no multiplicity adjustment for the testing of the secondary endpoints. No formal hypothesis testing will be performed.

Secondary efficacy endpoint for clinical outcome and response at the TOC and FU Visits will be summarized using the ITT and micro-ITT NTF-S Populations. In addition, if the study stops for efficacy, a summary of clinical outcome and response at the TOC visit will be performed on the micro-ITT NTF-S (IA Set) Population.

Secondary efficacy endpoints for participant-level microbiological outcome and response at the TOC and FU Visits, as well as therapeutic response at the FU Visit, will be summarized using the micro-ITT NTF-S Population. In addition, if the study stops for efficacy a summary of participant-level microbiological outcome and response at the TOC visit will be performed on the micro-ITT NTF-S (IA Set) Population.

The 95% Exact CI Clopper-Pearson for microbiological, clinical, and therapeutic success rate will be included by treatment group. For participant level response, the MN weighted success rate difference (via actual stratification) will be calculated along with the 95% CI (using MN method adjusting for treatment and actual pooled strata). Reasons for failure (including receipt of non-study antibacterial therapy for uUTI) will be summarized for each treatment group for all participants that are failures.

Supportive analyses to assess the homogeneity of the treatment difference across analysis strata will be implemented as in the primary efficacy analysis. This will also include the components of the primary composite endpoint of clinical response and micro response at TOC for the primary population (micro-ITT NTF-S (IA Set) if the study stops for efficacy else the micro-ITT NTF-S Population).

Separately, percent of clinical outcomes by visit will be plotted for the ITT Population, and percent of participant level microbiological outcomes by visit will be plotted for the micro-ITT/NTF-S/NTF-NS Populations.

7.2.6.2. Sensitivity Analyses

Sensitivity analyses will be performed to investigate the robustness of the secondary estimands for microbiological response at TOC and FU, clinical response at TOC and FU, as well as therapeutic response at FU in their corresponding analysis populations defined in Section [7.2.6.1](#). Success rate between treatment groups (gepolidacin – nitrofurantoin) will be analyzed using unadjusted difference and corresponding two-sided 95% CI (using MN method adjusting for treatment only) will also be presented.

7.2.6.3. Supplementary Analyses

Supplementary analyses will be performed on secondary endpoints including:

An analysis of therapeutic response at FU will be performed in the micro-ITT and micro-ITT NTF-NS and in the ME-FU/NTF-S/NTF-NS Populations.

An analysis of clinical outcome and response by visit will be performed in the CE-TOC, CE-FU, micro-ITT, and micro-ITT NTF-NS Populations.

An analysis of microbiological outcome and response by visit will be performed in the micro-ITT, micro-ITT NTF-NS, ME-TOC/NTF-S/NTF-NS, and ME-FU/NTF-S/NTF-NS Populations.

Success rate between treatment groups (gepotidacin – nitrofurantoin) will be analyzed using unadjusted difference and corresponding two-sided 95% CI (using MN method adjusting for treatment only) will also be presented. Reasons for failure (including receipt of non-study antibacterial therapy for acute cystitis) will be summarized for each treatment group for all participants that are failures.

7.2.6.4. Subgroup Analyses

Subgroup analyses of each secondary endpoint (participant-level therapeutic response, participant-level clinical outcome / response, and participant-level & uropathogen-level microbiological outcome / response, at the relevant visit) will be performed as listed in [Table 12](#). See [Section 5.4.2](#) for the definition of subgroups. For qualifying uropathogen thresholds, see [Section 7.3.2](#). All subgroup analyses will follow the same layout/content contained in the original presentation of the main analyses. The population will include complete trial data (i.e., including participants in the IA Set and overrun if the study stops early for efficacy). Summary Tables will be paginated by each subgroup level, and only the unadjusted difference and its 95% CI (using MN method adjusting for treatment only) in success rate will be presented.

Table 12 Subgroup and Uropathogen Level Analyses

Analysis/Endpoint Description: Therapeutic Response	
Visit: FU	
Population	Subgroup
micro-ITT	Qualifying uropathogen species/group (including phenotypic and genotypic subcategories), by age category (<18, ≥18 to 50, >50), acute cystitis recurrence (nonrecurrent infection, recurrent infection), stratification combinations (age group and acute cystitis recurrence), region, race, ethnicity, baseline clinical symptom score, menopausal status, number of qualified uropathogens at Baseline
micro-ITT NTF-S	Qualifying uropathogen species/group (including phenotypic and genotypic subcategories), by age category (<18, ≥18 to 50, >50),

Analysis/Endpoint Description: Therapeutic Response	
Visit: FU	
	acute cystitis recurrence (nonrecurrent infection, recurrent infection), stratification combinations (age group and acute cystitis recurrence), region, race, ethnicity, baseline clinical symptom score, menopausal status, number of qualified uropathogens at Baseline
micro-ITT NTF-NS	Qualifying uropathogen species/group (including phenotypic and genotypic subcategories), by age category (<18, ≥18 to 50, >50), acute cystitis recurrence (nonrecurrent infection, recurrent infection), stratification combinations (age group and acute cystitis recurrence), region, race, ethnicity, baseline clinical symptom score, menopausal status, number of qualified uropathogens at Baseline
ME-FU	Qualifying uropathogen species/group (including phenotypic and genotypic subcategories), by age category (<18, ≥18 to 50, >50), acute cystitis recurrence (nonrecurrent infection, recurrent infection), stratification combinations (age group and acute cystitis recurrence), region, race, ethnicity, baseline clinical symptom score, menopausal status
ME-FU NTF-S	Qualifying uropathogen species/group (including phenotypic and genotypic subcategories), by age category (<18, ≥18 to 50, >50), acute cystitis recurrence (nonrecurrent infection, recurrent infection), stratification combinations (age group and acute cystitis recurrence), region, race, ethnicity, baseline clinical symptom score, menopausal status
ME-FU NTF-NS	Qualifying uropathogen species/group (including phenotypic and genotypic subcategories), by age category (<18, ≥18 to 50, >50), acute cystitis recurrence (nonrecurrent infection, recurrent infection), stratification combinations (age group and acute cystitis recurrence), region, race, ethnicity, baseline clinical symptom score, menopausal status
Analysis/Endpoint Description: Clinical outcome and response	
Visit: TOC/FU	
ITT	Age category (<18, ≥18 to 50, >50), acute cystitis recurrence (nonrecurrent infection, recurrent infection), stratification combinations (age group and acute cystitis recurrence), region, race, ethnicity, baseline clinical symptom score, menopausal status
CE-TOC CE-FU	Age category (<18, ≥18 to 50, >50), acute cystitis recurrence (nonrecurrent infection, recurrent infection), stratification combinations (age group and acute cystitis recurrence), region, race, ethnicity, baseline clinical symptom score, menopausal status
micro-ITT	Qualifying uropathogen species/group (including phenotypic and genotypic subcategories)

Analysis/Endpoint Description: Therapeutic Response	
Visit: FU	
micro-ITT NTF-S	Age category (<18, ≥18 to 50, >50), acute cystitis recurrence (nonrecurrent infection, recurrent infection), stratification combinations (age group and acute cystitis recurrence), region, race, ethnicity, baseline clinical symptom score, menopausal status, qualifying uropathogen species/group (including phenotypic and genotypic subcategories)
micro-ITT NTF-NS	Qualifying uropathogen species/group (including phenotypic and genotypic subcategories)
Analysis/Endpoint Description: Participant-level Microbiological outcome and response	
Visit: TOC/FU	
micro-ITT NTF-S	Age category (<18, ≥18 to 50, >50), acute cystitis recurrence (nonrecurrent infection, recurrent infection), stratification combinations (age group and acute cystitis recurrence), region, race, ethnicity, baseline clinical symptom score, menopausal status,
Analysis/Endpoint Description: Uropathogen-level Microbiological outcome and response	
Visit: TOC/FU	
micro-ITT	All qualifying uropathogens and by qualifying uropathogen species/group (including phenotypic and genotypic subcategories)
micro-ITT NTF-S	All qualifying uropathogens and by qualifying uropathogen species/group (including phenotypic and genotypic subcategories)
micro-ITT NTF-NS	All qualifying uropathogens and by qualifying uropathogen species/group (including phenotypic and genotypic subcategories)
ME-TOC ME-FU	All qualifying uropathogens and by qualifying uropathogen species/group (including phenotypic and genotypic subcategories)
ME-TOC NTF-S ME-FU NTF-S	All qualifying uropathogens and by qualifying uropathogen species/group (including phenotypic and genotypic subcategories)
ME-TOC NTF-NS ME-FU NTF-NS	All qualifying uropathogens and by qualifying uropathogen species/group (including phenotypic and genotypic subcategories)

Percent of therapeutic success at FU overall and by qualifying uropathogen by visit will also be plotted for each treatment group for the micro-ITT NTF-S Population.

Forest plot for therapeutic success rate at FU overall and by subgroup will be plotted for micro-ITT/NTF-S/NTF-NS Populations.

Forest plot for clinical success rate at each visit (TOC, FU) overall and by qualifying baseline uropathogen and uropathogen phenotypic and genotypic subcategories for the micro-ITT/NTF-S/NTF-NS Populations. Stacked bars of clinical outcome at each visit (OT, TOC, FU) will be plotted for ITT Population.

Forest plot for participant level microbiological success rate and uropathogen level microbiological success rate by qualifying baseline uropathogen and uropathogen phenotypic and genotypic subcategories will be plotted for the micro-ITT/NTF-S/NTF-NS Populations at each visit (TOC, FU). Stacked bars of participant level microbiological outcome and uropathogen level microbiological outcome by qualifying baseline uropathogen at each visit (OT, TOC, FU) will be plotted for micro-ITT/NTF-S/NTF-NS Populations.

CCI

CCI

CCI

CCI

CC

CCI

CCI

CCI

CCI

CCI

CCI

